Randomization Procedure 1. Participants will be stratified by age groups (10-14, 15-19, and 20-29) and event type (ideation, attempt, binge + recent ideation), then randomized to the control or intervention condition using a 1:1 assignment ratio. Re-randomization of all participants will occur again at **CM3** (another 30 days or 60 days/2 months post-baseline assessment).

Control Condition: Monitoring and Case Management (CM): Research Program Assistants, who are trained Surveillance System Staff, will conduct the monitoring and case management visits in participants' homes or other private settings at baseline, 1, 2, 3 and 6 months post-enrollment. This time-period was selected as the highest risk period for a subsequent suicide event following an initial episode.[12, 13] The CM visit includes rapport-building, use of the Suicide Ideation Questionnaire (SIQ) to assess imminent risk, and if youth report not yet having connected to services, referral to Apache Behavioral Health Services (ABHS), the local community mental health center. As we have added opioid related questions through an administrative supplement, the monitoring and case management visits will also allow us to track any safety concerns related to opioids and provide appropriate referrals to treatment. If minors seek treatment elsewhere or express disinterest, case managers will also facilitate connections to other care providers

(traditional healers, church, IHS social services/mental health, and private providers). At CM visits, the **Research Program Assistants will also monitor participants' completion of the study battery**, which will be self-administered using tablets. In addition, Research Program Assistants will score the SIQ before leaving the youth. If the SIQ reveals the participant is at imminent risk, Research Program Assistants will employ a protocol for rescue services (*described below*), which involves triaging youth immediately to the ED for further assessment and care.

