Intervention 1: New Hope is based on a brief empirically-validated Emergency Department (ED) intervention.[14-17] Our intervention, adapted with strong guidance from a Community Advisory Board (CAB), was designed to be implemented over 1 visit (2-4 hours) in a youth-preferred setting after ED discharge for a suicide attempt, and in the past few years has been updated to also target suicide ideation and binge behavior, including substance use more generally which could encompass opioids. Note: the intervention does not however focus directly on opioid use. NH emphasizes the seriousness of a suicide attempt; teaches coping skills to reduce risk, including emotion regulation, cognitive restructuring, social support, and safety planning; and helps participants overcome barriers to treatment motivation, initiation, and adherence. A center-piece of the intervention is a 20-minute video produced by WMAT-CAIH with Native actors, vignettes specific to this community, and Elders speaking in Apache (with sub-titles) about the seriousness of suicide, its impact on the community, their concern for the adolescent, and beliefs about the communal importance of each individual's life. **Youth are encouraged to choose a support person from his/her family to take part in the intervention because surveillance data indicated family conflict was one of the major reasons reported for suicide events and family members can reinforce skills including the youth's safety plan.**[17-19] The oral consent script for family members participating in New Hope will be used to introduce the intervention to the family member. NH is psychoeducation to supplement and promote mental health services, while encouraging connections to traditional healers and caring adults.[5] NH will be provided by CMHWs (and not Research Program Assistants) to reduce potential bias in the assessments. Intervention sessions will be recorded for quality assurance purposes. Two trained raters will use a standardized form to rate various components of the intervention session including—if all components of the lesson were delivered, the quality of delivery and the relationship between facilitator and participant.

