After 30 days from CM3, all youth will be visited by Research Program Assistants and complete a fourth assessment (CM4). The 30-day time frame between CM3 and CM4 will allow ample time to complete the ER intervention with participants and assess any changes in resilience across study groups. To track long-term outcomes, all youth will complete a final assessment 3 month later (CM5: 6 months post-enrollment). All youth will be followed to the end of the study period (up to 4.75 years from the first participant’s enrollment) for any subsequent suicide events using the Apache surveillance system. If necessary, assessments may be conducted over the phone for participants who start in the study but are located elsewhere during an assessment timepoint.

As part of the economic evaluation supplement, our staff will be asked to fill out time logs listing how they spent time the preceding day. This will not affect the study participants in any way.

Aim 3: STUDY PROCEDURE

If stakeholders provide informed consent, they will be interviewed by Drs. [name] or [name] using a semi-structured guide to gather their views on the Southwest Hub’s key intervention components (Surveillance/Case Management, New Hope and Elders’ Resilience Interventions). They will also be asked to participate in a 2x annually administered online survey to better understand how capacity for sustainability changes over time. If they consent to the online survey, the Program Sustainability Assessment Tool (PSAT) will be administered via email to participants every six months.

2. Describe the number and type of study visits and/or contacts between the study team and the participant, how long they will last, and where/how they will take place.

Aim 1: Five study visits will take place over the course of 6 months. All study visits will take place in the participants' home or a private location.

CM1: Recruitment, consent, randomization, baseline assessment: 2 hours

Intervention Group: NH: 2-4 hours

CM2: Assessment: 1 hour

CM3: Assessment and randomization: 1 hour

Intervention Group: EC: 2-4 hours

CM4: Assessment: 1 hour

CM5: Assessment: 1 hour

Opioid Data Collection Sub-Study (for a subset): Additional 60-90 minutes interview

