The ASSIST The World Health Organization (WHO) Alcohol, Smoking and Substance Involvement Screening Test (ASSIST) is a questionnaire that screens for all levels of problem or risky substance use in adults.[44] A risk score can be provided for each substance, and scores are grouped into 'low risk', 'moderate risk' or 'high risk'. It has been validated in youth and adolescents, as well as adults. [44]

For locally created items, During our initial research meetings we asked our team about changes they have observed in children as a result of the New Hope and Elders curriculum. We then generated a list of items to include on the research study to help in capturing locally relevant changes in youth's thoughts, feelings and behaviors that could occur as a result of the interventions under study.

For opioid related items, we consulted with other researchers examining substance use in Native American populations to compile our list of questions (see Appendix). The questions we included have been used and validated in other studies with Native American populations (e.g., Monitoring the Future study), as well as come from national surveys (e.g., 2015 NSDUH Survey, CDC National HIV Behavioral Surveillance).

Exit Interview Questions: Additional questions asked during the last case management visit about the participant's overall experience in the study and their experience with the interventions (if applicable)

Session Summary Form: Administered after each study visit to better understand what happened between sessions and during sessions.

Additional Case Management Form: Administered during additional case management visits to better understand what happens during those interactions with participants

Work Absenteeism: For participants 16 and over who are not enrolled in school to better understand work performance for use in the costing analysis (Economic Evaluation Supplemental Aim).

PROMIS Pediatric Anxiety Short Form: For all participants, includes 8 items assessing symptoms of generalized anxiety disorder.

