C. If genetic/genomic analyses are planned, address whether the data will be contributed to a GWAS or other large dataset. Address returning unanticipated incidental genetic findings to study participants.

N/A

D. If clinical or laboratory work will be performed at JHU/JHH, provide the JH Biosafety Registration Number.

N/A

E. If you will perform investigational or standard diagnostic laboratory tests using human samples or data, clarify whether the tests are validated and/or the lab is certified (for example is CLIA certified in the U.S.). Explain the failure rate and under what circumstances you will repeat a test. For all human testing (biomedical, psychological, educational, etc.), clarify your plans for reporting test results to participants and/or to their families or clinicians. Address returning unanticipated incidental findings to study participants.

N/A

F. If your study involves medical, pharmaceutical or other therapeutic intervention, provide the following information:

Answers for this section apply only to Aim 1. Aim 3 does not involve an intervention.

a. Will the study staff be blind to participant intervention status?

Yes.

b. Will participants receive standard care or have current therapy stopped?

All participants will receive standard of care, which is case management visits and referrals to care. Participants may still receive this care post study.

c. Will you use a placebo or non-treatment group, and is that justifiable?

We will use a control group who will receive case management and will be referred to mental health care—the standard protocol for the existing Apache system.

d. Explain when you may remove a participant from the study.

Participants will be removed from the study if they move off reservation or are relocated for treatment.

e. What happens to participants on study intervention when the study ends?

The interventions are intended to be brief (2-4 hours). During the intervention and case management visits youth will become acquainted with available local resources, including visits by CMHVs.

f. Describe the process for referring participants to care outside the study, if needed.

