An imminent risk procedure was developed by WMAT-CAIH as part of previous studies to ensure triage and access to emergency care for youth who are at immediate risk for suicide. This procedure was approved by Tribal, Hopkins and IHS IRBs, and will be employed by CMHWs for this project (see *Protection of Human Subjects*). At the close of each visit, youth will complete the Suicide Ideation Questionnaire (SIQ/SIQ-JR) (see *Appendix*). CMHWs immediately score SIQ at the time of visit, and depending on score will respond in a graduated fashion. The staff member also has the training and discretion to recognize high risk individuals and will act accordingly, even if SIQ does not indicate risk.

c. Identified to be Using or Abusing Opioids:

If current opioid use is identified through our supplement, a two-fold strategy will be used. First, once opioid related items are approved to be added to the surveillance system, substance specific referrals and case management will be covered by the surveillance system. Second, an additional opioid abuse assessment will be conducted to ensure the safety of participants in the SMART trial who endorse current or recent use. This assessment would be conducted *at the study visit*. This assessment will allow the study team to determine if

the participant can continue in the trial, in addition to get them into the most appropriate treatment. All participants who endorse opioid use will receive referrals.

d. Risk of a Breach in Confidentiality

There are two methods by which participants' confidentiality can be breached, including inadequate safeguards of the collected data and a direct breach of confidentiality by study personnel. The consent form will describe in detail the methods used to protect participants' confidentiality and those individuals and entities (i.e., Johns Hopkins IRB, NIH) that have access to the data. As mentioned above, we will obtain a Certificate of Confidentiality for this study. We will explain to the participants that we will have obtained this Certificate of Confidentiality as added protection for their privacy.

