Dangerousness to self; suicide thoughts or attempts. We recognize that this population is high risk and have developed a risk management protocol that has been approved by the community and our partner IRBs and successfully implemented in several previous studies (e.g., NARCH III 1S06 GM074004; SAMHSA 5 SM057835) with suicidal youth from this community. As part of the first assessment visit, participants will be questioned about medical, behavioral or psychological events since the last visit, and Research Program Assistants will administer the SIQ to monitor and assess risk. In addition, as the participant completes the assessments, Research Program Assistants will note participant responses that indicate concern. Research Program Assistants will be required to review disclosure information with the local PD ([name]) and, if deemed necessary, conduct follow-up inquiry with the participant to further determine level of risk and call one of the PIs to review the information. Our response to each such event will be graded and proportionate. If the SIQ score is above the clinical cutoff as determined by the measurement developers, the SIQ-Past Few Days (SIQ-PFD) is administered. For immediate risk for suicide (i.e., active ideation with a plan and unwillingness to cooperate with a mental health referral as assessed by the SIQ-PFD and follow-up inquiry), Research Program Assistants will be trained to secure the immediate safety of the participant, engage the

participant's parent, and call the police and then the PI and local PD. At the lowest level of suicidal ideation (i.e., passive ideation without plan, no interest in dying and willing to cooperate with a mental health referral as assessed by the SIQ-PFD and follow-up inquiry), Research Program Assistants will conduct safety planning, engage the parent/guardian and provide a mental health referral as soon as possible.. *Please note safety plans are developed with all participants (and reviewed with their parents) who score above the clinical cut-off for the SIQ, and/or whom the research staff have concerns about.*

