E. Describe how participant privacy will be protected during data collection if sensitive questions are included in interviews.

Aim 1: Participant privacy will be protected by completing questionnaires on tablets in a private location of the participants' choosing. Data will be held in a secure, password protected database. Only CMHWs will have access to the data. Privacy for minors will be protected including reporting of high risk behaviors such as past or current opioid use. Study data will not be shared with participant's legally authorized representative unless there is evidence that the participant is a danger to him/herself including from opioid addiction, danger to others, or if there is confirmed or suspected abuse or neglect of the participant. Research staff will work to ensure the safety of the participant, and in acute situations, will act immediately to involve parents and appropriate authorities. In the case of opioid use that does not warrant breaking privacy protections but would benefit from treatment or prevention strategies, research staff will encourage both adult and youth participants to disclose their use to parents with research staff support in order to engage a familial support system for youth related to opioids. Communication between investigators and participants will be conducted in-person or by phone versus in writing (i.e., email) to further protect privacy by limiting additional paper or electronic documentation that could be more easily breached.

Aim 3: There are no sensitive questions included in the interviews.

VIII. Direct Personal and Social Benefits:

A. Describe any potential direct benefits the study offers to participants (“payment” for participation is not a direct personal benefit).

Aim 1: Participants may benefit from the interventions by experiencing a reduction in their suicidal thoughts or binge behaviors, and an increase in coping skills and resilience.

Aim 3: Participants will be able to voice challenges to implementation and scale-up of suicide prevention and resilience promotion programs.

B. Describe potential societal benefits likely to derive from the research, including value of knowledge learned.

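### The protocol answers yes to staff blinding, but this cannot hold for the staff who deliver the interventions, and no described procedure supports it for those who collect the SIQ

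*Combined protocol and SAP*

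**What the plan says.** The blinding question in Section V.C.5.F.a ("Will the study staff be blind to participant intervention status") is answered with a single affirmative word. The section states that its answers apply to Aim 1 only. It does not say which staff are meant, how they are kept blind, or whether this is checked.

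Section V.C.1 gives the assessment role to the Research Program Assistants, who "will conduct the monitoring and case management visits" at baseline and at 1, 2, 3 and 6 months. It gives delivery to other staff: "NH will be provided by CMHWs (and not Research Program Assistants) to reduce potential bias in the assessments". Elders' Resilience is likewise given to a separate CMHW working with an Elder, for the same stated reason.

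Both randomisations are placed inside assessment visits. Section V.C.2 lists randomisation among the contents of CM1, and for the second allocation reads "CM3: Assessment and randomization: 1 hour".

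The safety sections describe the roles differently. Section VII.C.b says "CMHWs immediately score SIQ at the time of visit", and Section VII.E says "Only CMHWs will have access to the data".

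**The concern.** The SIQ is a subjective scale, collected face to face and scored on the spot. A staff member who knows the allocation can influence how the questionnaire is introduced, how hesitation is handled and how answers are followed up, without intending to. The protocol accepts this risk, since avoiding assessment bias is its stated reason for separating delivery from assessment. If the blinding answer is carried into a report, readers will credit the trial with a protection that its procedures do not provide. If the safety sections are followed as written, the group that delivers the interventions scores the primary outcome.

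**Working it through.** The plan gives no figure to reproduce here, so the check sets its sections side by side.

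1. **All study staff.** Section V.C.1 has CMHWs deliver New Hope, and a CMHW with an Elder deliver Elders' Resilience. They know what they delivered. Taken literally, the answer is false.

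2. **Assessors only.** The assistants give the baseline assessment at CM1, and the first randomisation happens at that same visit (V.C.1). The second happens at CM3. Section V.C.5.A, which is meant to explain assignment, gives strata, ratio and timing. Neither it nor any other section says who performs the assignment, who holds the allocation list, or how the result is kept from the assistant present.

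3. **Order within the visit.** Section V.C.1 puts the baseline assessment before randomisation, while the V.C.2 list names randomisation first. Sections V.C.5.F.f, VII.C.b and X.C.1 place the SIQ at the close of visits. The text therefore does not secure that the CM1 and CM3 SIQ precede that visit's allocation.

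4. **Exposure.** Table 2 schedules the SIQ at five visits. Those after the first allocation are CM2 to CM5, so 4 of 5. Those after the second are CM4 and CM5, so 2 of 5.

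5. **Items that reveal allocation.** Section III.A adds battery items on participants' time in the interventions. A Session Summary Form is due at CM2 to CM5 (V.C.4, Table 2), with no administrator named. Exit questions about the interventions come at CM5.

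6. **Who scores the SIQ.** Sections V.C.1 and X.C.1 say the assistants. Section V.C.5.F.f says CMHVs, an abbreviation that the protocol does not define, and VII.C.b says CMHWs.

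7. **How the SIQ is completed.** Sections V.C.1 and VII.E describe self-completion on a tablet. Section X.C.1 has the assistants complete it together with participants. Section V.C.1 also allows assessment by telephone without saying how self-completion would then work. Even on a tablet, the assistant scores the answers before leaving, so they are not private from the assessor.

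8. **Size.** Section III.B gives a benchmark for an SIQ change that matters: a 25% fall from an expected baseline of 45, or 0.25 × 45 = 11.25 points. Nothing in the documents says how far an assessor's knowledge of allocation moves a score, so no bias can be computed.

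**The case against.** The strongest defence is that the plan separates delivery from assessment and has the battery self-completed on tablets, which limits what an assessor can do. Totalling a self-completed scale is arithmetic. The CMHW scoring passages describe a risk-triage procedure carried over from previous studies and may use job titles loosely. The sentence restricting data access to CMHWs cannot be literal, because Section VII.C.d gives database access to study coordination staff and X.A.1 assigns analysis to investigators. All of this stands as mitigation. It does not amount to blinding, and it does not make the affirmative answer correct.

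A reader might infer several stronger things that the documents do not support:

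- **That the assistants randomise participants.** Every sentence on randomisation is passive. Central or concealed assignment is not described, but it is not excluded.
- **That there is no protection at all.** Separate delivery staff and tablet completion are real safeguards.
- **That the exit questions unblind the whole follow-up.** They occur only at CM5 and cannot affect CM2 to CM4.
- **That staff administer the SIQ throughout.** The sentence "Research Program Assistants will administer the SIQ to monitor and assess risk" is tied to the first assessment visit, and administering can mean handing over a tablet.
- **That a participant's own interventionist scores that participant's SIQ.** The conflict concerns staff groups. No section says this happens for an individual participant.
- **That a bias of so many SIQ points can be stated.** Any such range would have no source in the plan.

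It is also fair to say that participants know what they received and report the outcome themselves. Blinding the assessors would not remove that source of bias, which is a further reason not to claim blinding without qualification.

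**Conclusion.** The blinding statement is wrong as written. It is false for the staff who deliver the interventions and has no described procedure behind it for the assistants who collect and score the SIQ. The text also contradicts itself on who scores the primary outcome and how it is completed, which weakens the plan's own safeguard. The bias cannot be quantified. What can be stated is the exposure: 4 of 5 SIQ assessments follow the first allocation and 2 of 5 follow the second.

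The conclusion assumes that no concealment procedure exists in a manual outside these documents. If one does, the assistants could be blind in part, but the unqualified answer would still be wrong for the CMHWs and Elders.

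**What to change.** - **Statement.** Replace the one-word answer in V.C.5.F.a with a role-by-role statement: participants and interventionists are not blind; outcome assessors are kept unaware of allocation as far as possible. Do not describe the trial as blinded without that qualification.
- **Allocation.** Name who assigns and who holds the list. Release the CM1 and CM3 results only after that visit's research battery is submitted, and only to staff who do not assess that participant.
- **Order of items.** Have the research SIQ and resilience scales self-completed on the tablet, with time-use, session-summary and exit items after them. State how this works for telephone assessments.
- **Consistency.** Reconcile V.C.1 and X.C.1 with V.C.5.F.f, VII.C.b and VII.E on who scores the SIQ and who holds outcome data. Where the same SIQ serves both research and suicide-risk triage, the safety procedure, including its timing and who carries it out, is for the sponsor to decide.

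The cost is protocol wording, data-system access rights, item order and some scheduling effort. Participants will sometimes reveal their allocation to assessors; log these occasions so that they can be reported.
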